Impact of uterine fibroids on symptoms, activities and health-related quality of life as measured by components of the UFS-QoL	
 Change from Baseline to Week 24 in the UFS-QoL Symptom Severity Scale score Change from Baseline to Week 24 in the UFS-QoL Activities Scale score Change from Baseline to Week 24 in the UFS-QoL Revised Activities Scale score Proportion of responders who achieved a meaningful increase of at least 20 points from Baseline to Week 24 in UFS-QoL Revised Activities Scale score Proportion of responders who achieved a meaningful reduction of at least 20 points from Baseline to Week 24 in UFS-QoL Bleeding and Pelvic Discomfort Scale score Change from Baseline to Week 24 in the interference of uterine fibroids with physical activities based on UFS-QoL Question 11 Change from Baseline to Week 24 in the interference of uterine fibroids with social activities based on UFS-QoL Question 20

Statistical Analysis Plan
Amendment 1: Effective June 14, 2019

MVT-601-3001 and 3002

Objective(s)	Endpoint(s)
	
 Change from Baseline to Week 24 in embarrassment caused by uterine fibroids based on UFS-QoL Question 29
Patient global assessment for function and symptoms as measured by the PGA for function and symptoms	
 Change in PGA for uterine fibroid related function from Baseline to Week 24 Change in PGA for uterine fibroid symptoms from Baseline to Week 24 Proportion of patients achieving improvement from Baseline in PGA for uterine fibroid symptoms from Baseline to Week 24 Proportion of patients achieving improvement from Baseline in PGA for uterine fibroid related function from Baseline to Week 24
Impact of heavy menstrual bleeding on social, leisure, and physical activities as measured by the Menorrhagia Impact Questionnaire	
 Change from Baseline to Week 24 in the Menorrhagia Impact Questionnaire Score for physical activities Change from Baseline to Week 24 in the Menorrhagia Impact Questionnaire Score for social and leisure activities
Pain associated with uterine fibroids ^b	Proportion of women who achieve a maximum NRS score for pain associated with uterine fibroids over the last 35 days of treatment that is at least a 30% reduction from Baseline in the subset of women with a maximum pain score ≥ 4 during the 35 days prior to randomization
Safety	

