$$\text{Transformed Score} = [(\text{Highest possible score} - \text{Actual raw score}) / (\text{Possible raw score range})] * 100$$

For revised activities, the proportion of patients who are responders (defined as meeting a meaningful change from Baseline in the revised activity score) at Week 24 will be analyzed similarly to that for the change in BPD Scale score between the two treatment arms (relugolix + E2/NETA and placebo). The proposed responder threshold is a 20-point increase. Details of the determination of the meaningful change in the Revised Activities Scale score can be found in [Appendix 5](#).

Missing Items

For any scale analyses, if < 50% of the scale items are missing, the scale should be retained using the mean scale score of the items present. If ≥ 50% of the items are missing, no scale score should be calculated; the subscale score will be considered missing.

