Sustained amenorrhea rate by visit	mITT	Cochran-Mantel-Haenszel test	P < 0.05	Monthly	Frequency and percentages
Proportion of women with a hemoglobin below the lower limit of normal at Baseline who achieve an increase of ≥ 1 g/dL from Baseline at Week 24	mITT	Cochran-Mantel-Haenszel test	P < 0.05	Monthly	Frequency and percentages
Change (absolute and %) from Baseline to Week 24 in hemoglobin for women with a hemoglobin ≤ 10.5 g/dL at Baseline	mITT	Mixed-effects model	P < 0.05	Monthly	LS means for % change
Proportion of women who achieve a maximum Numerical Rating Scale score for uterine fibroid-associated pain over the last 35 days of treatment that is at least a 30% reduction from Baseline in the subset of women with a maximum pain score ≥ 4 during the 35 days prior to randomization	Subset of mITT	Cochran-Mantel-Haenszel test	P < 0.05	Week 12, 24	Frequency and percentages
Mean maximum NRS scores over time	Subset of mITT	Descriptive		Monthly	Means
Proportion of responders who had meaningful reduction of >20 points from Baseline to Week 24 in UFS-QOL Bleeding and Pelvic Discomfort Scale (Q1, Q2 and Q5)	mITT	Cochran-Mantel-Haenszel test	P < 0.05	Week 12, 24	Frequency and percentages
Proportion of responders who had meaningful increase of > 20 points from Baseline to Week 24 in UFS-QOL revised activities	mITT	Cochran-Mantel-Haenszel test	P < 0.05	Week 12, 24	Frequency and percentages

Secondary Endpoints	Analysis Population	Statistical Method/Test	Declare Statistical Significance ^a	Time Points of Summary	Summary Statistics
Change from Baseline to Week 24 in impact of uterine fibroids based on the UFS-QOL revised activities domain	mITT	Mixed-effects model	P < 0.05	Week 12, 24	LS means for change
Change from Baseline to Week 24 in impact of uterine fibroids based on the UFS-QOL activities domain	mITT	Mixed-effects model	P < 0.05	Week 12, 24	LS means for change
Change from Baseline to Week 24 in the interference of uterine fibroids with physical activities based on UFS-QOL Q11	mITT	Mixed-effects model	P < 0.05	Week 12, 24	LS means for change
Change from Baseline to Week 24 in the interference of uterine fibroids with social activities based on UFS-QOL Q20	mITT	Mixed-effects model	P < 0.05	Week 12, 24	LS means for change
Change from Baseline to Week 24 in embarrassment caused by uterine fibroids based on UFS-QOL Q29	mITT	Mixed-effects model	P < 0.05	Week 12, 24	LS means for change

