APPENDIX 5. ESTIMATION OF RESPONDER THRESHOLD FOR THE UFS-QOL REVISED ACTIVITIES SCALE

5.1. Approach to Estimating the Responder Threshold of the Revised Activities Scale

The Uterine Fibroid Symptom and Health-Related Quality of Life (UFS-QoL) Revised Activities Scale includes five of the seven most relevant items pertaining to physical and social activities ([Coyne 2018](#)). These are:

During the previous 3 months, how often have your symptoms related to uterine fibroids:

- Interfered with your physical activities?
- Made you decrease the amount of time you spent on exercise or other physical activities?
- Made you feel that it was difficult to carry out your usual activities?
- Interfered with your social activities?
- Caused you to plan activities more carefully?

Response options include:

- None of the time;
- A little of the time;
- Some of the time;
- Most of the time;
- All of the time.

The summary score of the five items ranges from 0 to 100, where a lower score indicates a higher ability to do activities (ie, lower score = good) and a higher score indicates a lower ability to do activities.

Change from Baseline to Week 24 in the Revised Activities Scale score is a secondary endpoint of the pivotal studies (MVT-601-3001 and MVT-601-3002) to evaluate the treatment benefit of relugolix + E2/NETA (Group A) compared with placebo (Group C). Additionally, a responder analysis will be performed between the two groups with respect to the proportion of patients who have achieved a meaningful reduction from Baseline to Week 24 in the Revised Activities Scale.

The approach used to derive the responder threshold for improvement in the Revised Activities Scale is similar to that used for the Bleeding and Pelvic Discomfort (BPD) scale (see details in Appendix 4).

This appendix briefly describes the quantitative and supportive qualitative methods and summarizes the respective analysis results.

The meaningful change threshold is the smallest reduction in the Revised Activities Scale score that is considered meaningful by patients ([Cohen, 1988; Crosby, 2003; Revicki, 2008; Wyrwich, 2013; Cappelleri, 2014; Coon, 2018](#)). The magnitude of a meaningful change threshold depends

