5.3.3. Estimation of Responder Threshold

Using the mean value for measuring improvement in the Revised Activities Scale would yield estimates that are conservative because expected values do not necessarily constitute a *minimum* meaningful change threshold for patients. That is, nearly half the patients stratified in the PGA “1-category improvement” who reported changes smaller than the mean on the Revised Activities Scale would be classified as nonresponders by using the mean as the threshold despite of their reporting “1-category improvement”. A less conservative, though still plausible estimate for the minimal meaningful change threshold is the lower bound of the 95% CI for mean change in the “1-category improvement” group. Its use will result in a smaller proportion of patients being classified as nonresponders on the Revised Activities Scale than the expected value (ie, the mean). Similarly, one can also consider the median value since it is less influenced by outliers than either the mean or CI estimates.

According to the uncollapsed anchor-based analysis (Table 5.3-1), the median value for a “1-category improvement” is 20-points, while the lower bound 95% CI for this group is about 21-points (ie, a 21-point improvement on the revised activities between Baseline and Week 24). Given the large discrepancy between the mean and median values suggests that outliers were present in the data; hence, the median value is recommended as a potential minimum change threshold.

Examination of the CDF curves for the potential minimum meaningful threshold value of 20 points on the Revised Activities Scale allows one to estimate the cumulative percent of patients that would experience the improvement. As illustrated in Figure 5.3-2, approximately 38% of the “no change” group and 61% of the “1-category improvement” group experienced at least a 20-point improvement (eg, approximately 62% of the “no change” group and 39% of the “1-category improvement” group experienced less than a 20-point improvement to the left) on the Revised Activities Scale by Week 24.

Figure 5.3-2: Cumulative Distribution Function of Change at Week 24 in UFS-QoL Revised Activities Scale Score by PGA Anchor Change Category (Collapsed)

[figure not shown]

Abbreviations: PGA = patient global assessment.

As supportive information, the empirical CDFs with step-curves (reflecting the discrete nature of the revised activities scores) are provided (Figure 5.3-3), indicating that smooth curves are

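### The Revised Activities responder cut-off is at least 20 points in Table 1 but more than 20 in Appendix 1, and a change of exactly 20 can occur; Appendix 5 also states the direction of the scale wrongly in two places

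*SAP*

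**What the plan says.** All of the following stands in the current text (SAP Amendment 1).

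- **Section 1.1, Table 1** lists the endpoint as: "Proportion of responders who achieved a meaningful increase of at least 20 points from Baseline to Week 24 in UFS-QoL Revised Activities Scale score".
- **Appendix 1** lists the same endpoint as: "Proportion of responders who had meaningful increase of > 20 points from Baseline to Week 24 in UFS-QOL revised activities". It is to be tested by Cochran-Mantel-Haenszel at P < 0.05, with summaries at Weeks 12 and 24. Section 7.4 refers the reader to Appendix 1 for all secondary endpoints and their analyses.
- **Section 7.4.4.2** gives the number without an operator: "The proposed responder threshold is a 20-point increase". Appendix 5 Section 5.5 likewise speaks of a 20-point change.
- **Appendix 5 Section 5.3.3**, where the threshold is examined, reads off the share of each anchor group at or above the cut: about 38% of the no-change group and 61% of the one-category "group experienced at least a 20-point improvement".
- **Appendix 5 Section 5.1** describes a 0 to 100 score "where a lower score indicates a higher ability to do activities (ie, lower score = good" and a responder analysis of the "proportion of patients who have achieved a meaningful reduction from Baseline to Week 24 in the Revised Activities Scale". Section 5.2.3 also speaks of a reduction.

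**The concern.** A responder analysis needs one cut-off, fixed before unblinding. Here the objectives table and the analysis table give different ones, and the two remaining statements (Sections 7.4.4.2 and 5.5) carry no operator to settle the matter. A programmer working from Appendix 1 would code a different endpoint from one working from Table 1.

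On a continuous score the difference would be empty. This scale is coarse and 20 is one of its attainable values, so responder rates and the nominal test could differ. The direction wording in Appendix 5 adds a second, separate inconsistency in the section that introduces the responder analysis.

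**Working it through.** **Inputs.** Section 7.4.4.2: five items, raw sum 5 to 25, raw range 20, transformed score = (25 − raw) / 20 × 100, higher is better. Table 5.3-2: one-category improvement group n = 53, mean 27.92, SD 25.65; no-change group n = 71, mean 11.55, SD 28.51. Table 5.3-1: median change 20 in the one-category group. Section 5.3.3: about 61% of that group at or above 20.

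**Reproducing the plan's figures.**
- One-category group: SE = 25.65 / √53 = 3.52; with t(0.975, 52) = 2.007 the half-width is 7.07, so the 95% CI is 20.85 to 34.99 (stated 20.85, 35.0).
- No-change group, by the same formula: 4.80 to 18.30 (stated the same).
- Pooled two-sample t-test: pooled SD 27.33, difference 16.37, 95% CI 6.55 to 26.19, p = 0.0013 (stated 16.38; 6.55, 26.20; 0.0013).

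The group size of 53 used below is therefore consistent with the table.

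**Step size.** One raw point is worth 100 / 20 = 5 points. The attainable changes around the cut are 15, 20 and 25. A woman whose raw sum falls from 18 to 14 goes from (25 − 18) / 20 × 100 = 35 to (25 − 14) / 20 × 100 = 55, a gain of exactly 20. She responds under Table 1 and not under Appendix 1, where with complete items the smallest qualifying gain is 25.

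**Prorated scores.** Under the missing-item rule, a score from four items moves in steps of 100 / 16 = 6.25, and one from three items in steps of 100 / 12 = 8.33. If one visit is prorated and the other complete, exactly 20 is still attainable; if both are prorated, it is not. A gain such as 31.25 − 10 = 21.25 is also possible, so equating the strict rule with 25 or more holds for complete items only.

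**Bound from the median.** With n = 53 the median is the 27th ordered value, and it equals 20. Hence:
- at least 27 women have a change ≥ 20: 27/53 = 50.9% or more;
- at most 26 women have a change > 20: 26/53 = 49.1% or fewer;
- at least one woman sits exactly on the cut, so the proven gap is at least 1/53 = 1.9 percentage points.

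**Against the plan's 61%.** 0.61 × 53 = 32.3, or about 32 women. Setting 61% against 49.1% gives 61 − 49.1 = 11.9, about 12 percentage points.

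**Bleeding and Pelvic Discomfort (BPD) scale.** Table 1 and Appendix 1 differ in the same way for this scale. Its raw range is 12, so the step is 100 / 12 = 8.33 and the neighbours of 20 are 16.67 and 25. A change of exactly 20 cannot occur, even with one item prorated, so the mismatch has no numerical effect there.

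**Direction.** Sections 5.1 and 5.2.3 speak of a reduction, and Section 5.1 treats lower as better. Against them stand the formula and its explanation in Section 7.4.4.2 (higher is better), Section 5.2.3.2 (a positive change is a better outcome), Table 5.3-1 (all improved groups have positive mean changes) and footnote 6 in Section 5.4.3.2 (a higher score means less interference).

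**The case against.** The best case for leaving this alone is that little turns on it. The endpoint is in the group that Table 1 marks as not for hierarchical testing, and Section 7.2 makes its p-value nominal. No primary, key secondary or gate-keeping result changes. That stands, and it limits the weight of the point.

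A reader might infer a proven loss of at least 12 percentage points under the strict rule. The document does not support that. The 61% is given as approximate and read from a kernel-smoothed distribution function. On a smooth curve the probabilities of ≥ 20 and > 20 are the same, so it cannot measure how many women sit exactly at 20. Section 5.3.3 calls the smooth and empirical curves reasonably close, which makes 12 plausible but not a bound. Only the order-statistic result is exact.

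A reader might also take Section 5.1 as a third responder definition that counts worsening as response. It is not. Within that section lower is better and response is a reduction, so the section agrees with itself, and it attaches no number to the reduction. Worsening would count only if its wording were joined to the formula it contradicts. Table 1, Section 7.4.4.2 and Appendix 1, which all give both a number and a direction, say increase. What remains is a direction error in explanatory text.

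Finally, Section 5.3.3 reports a proportion at or above 20; it does not itself define the endpoint with an operator. That is correct: only Table 1 does so with ≥. But Section 5.3.3 shows how the cut was evaluated, and Section 5.5 recommends 20 as the minimum meaningful change. A strict rule would exclude the very change named as the minimum.

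**Conclusion.** The conflict between Table 1 and Appendix 1 is real and affects classification. In the target anchor group at least one woman (1.9 percentage points) changes status, and perhaps about 12 points' worth if the approximate 61% holds for the empirical distribution. The exact bound assumes that the printed median of 20 is unrounded and that it applies to the 53 women in Table 5.3-2.

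These figures describe one anchor category in blinded, pooled data from the first third of patients. They are not a treatment effect: a stricter cut would also remove women from the no-change group and from placebo, and neither the size nor the direction of the effect on the Cochran-Mantel-Haenszel comparison can be computed from the document. The consequence is confined to the responder rates and nominal p-value of one other secondary endpoint. The SAP's own derivation favours ≥ 20, so Appendix 1 is the outlier. The wrong scale direction in Sections 5.1 and 5.2.3 is a separate wording error that the rest of the document contradicts.

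**What to change.** - In Appendix 1, change > 20 to ≥ 20 in the Revised Activities row. Make the same change in the BPD row for consistency; it alters no result.
- In Section 7.4.4.2 and Appendix 5 Section 5.5, add the operator so that all places read as at least 20 points.
- In Appendix 5 Sections 5.1 and 5.2.3, state that a higher Revised Activities score is better and that response is an increase of ≥ 20 points, and remove the references to a reduction.

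The cost is SAP wording only, to be settled before unblinding. Data collection, sample size, alpha and the testing order are untouched.

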2.2. Psychometric Analyses Based on Phase 3 Data

The same pooled, blinded data from the first third of patients enrolled in either of the two phase 3 studies (MVT-601-3001 or MVT-601-3002) was used for the psychometric analyses of the BPD Scale. The objective was to psychometrically evaluate the new scale in terms of item performance, reliability, validity, and ability to detect change. Of note, for the analyses specified in this section, only data at Baseline and Week 12 were used. The following analyses were performed:

Item Level Analysis Assessing Ceiling and Floor Effects:

- A descriptive summary of the eight items in the UFS-QoL Symptom Severity Scale at Baseline was provided to examine item distributions and ceiling/floor effects. Low ceiling effects ($< 20\%$) and higher floor effects ($> 20\%$) were expected at Baseline

due to symptom severity of patients with uterine fibroids enrolled in the phase 3 studies.

Internal Consistency:

Internal consistency reliability was assessed for the BPD Scale at Baseline and Week 12 by calculating Cronbach's alpha. Generally, a Cronbach's alpha coefficient (α) ≥ 0.7 indicates an acceptable level of internal consistency.

Item Performance:

- Intercorrelation of items that contribute to the BPD Scale by means of item-total correlation was determined.
- Item discrimination index was assessed for each item based on 1) the BPD Scale scores at single time points, and 2) the change from Baseline to Week 12 in the BPD Scale score to determine the degree to which individual items were able to discriminate between less and more severe patients ([Cappelleri, 2014](#)).

Known-Groups Validity:

- Known-groups validity was assessed based on groups defined by Baseline PGA for symptoms severity (five levels). Descriptive statistics of the BPD Scale will be provided for each severity level.

Ability to Detect Change:

Evidence that the new scale can identify differences in scores over time in individuals or groups who have changed with respect to the measurement concept will be investigated by providing the following descriptive statistics:

- Within person change from Baseline to Week 12 in each item on the BPD Scale
- Standardized effect size statistic (SES) for change from Baseline to Week 12 in each item scale. The ability to detect change will be judged based on Cohen's recommendations: small change (SES = 0.20), moderate change (SES = 0.50), and large change (SES = 0.80).

APPENDIX 3. DERIVATION AND VALIDATION OF THE UFS-QOL BLEEDING AND PELVIC DISCOMFORT SCALE

Results described in this appendix are based on the analyses described in [Appendix 2](#).

3.1. Development of the Bleeding and Pelvic Discomfort Scale Using Exploratory and Confirmatory Factor Analysis

Exploratory factor analysis was conducted on data from the phase 2 study TAK-385/CCT-001 study (n = 216) and the arising factor structure was assessed in a confirmatory factor analysis using data from the phase 3 studies MVT-601-3001 and MVT-601-3002.

3.1.1. Exploratory Factor Analysis Using Phase 2 Data

Exploratory factor analysis results revealed a two-factor solution based on the Kaiser criterion (eigenvalues > 1) and factor loading > 0.40 criteria specified in the analysis plan (see [Appendix 2](#)). Factor 1 and Factor 2 had eigenvalues of 3.394 and 1.196, respectively ([Table 3.1-1](#)). Three items were found to load adequately onto Factor 1 with loadings greater than 0.40: Item 1 (Heavy Bleeding during Your Period), Item 2 (Passing Blood Clots during Your Period), and Item 5 (Feeling Tightness or Pressure in Pelvis; see [Table 3.1-2](#)). Two items loaded onto Factor 2 with loadings larger than the prespecified level: Item 6 (Frequent Urination in Daytime) and Item 7 (Frequent Nighttime Urination). Item 8 (Feeling Fatigued) showed a loading value on Factor 1 just below the prespecified threshold (0.399) and showed evidence of cross-loading with the Factor 2 (0.288). An additional factor with a moderate eigenvalue (0.62) was considered based the scree plot ([Figure 3.1-1](#)) and factor loadings of its associated items (Item 3: Fluctuation in Duration of Menstruation, 0.416; Item 4: Fluctuation in Length of Monthly Cycle, 0.995; [Table 3.1-2](#)).

Overall the results show support for a seven-item three-factor model. Due to multi-factor loading, Item 8 (Feeling Fatigued) remains a single-item symptom and is not scored as part of any factor.

Figure 3.1-1: Scree Plot and Variance Explained for UFS-QoL Symptom Severity Scale Factors in TAK-385/CCT-001

[figure not shown]

Table 3.1-1: Exploratory Factor Analysis for the UFS-QoL Symptom Severity Scale in TAK-385/CCT-001

Item	Eigenvalue	Difference	Proportion	Cumulative
1	3.394	2.198	0.816	0.816
2	1.196	0.576	0.288	1.104
3	0.620	0.458	0.149	1.253
4	0.162	0.332	0.039	1.292
5	-0.170	0.114	-0.041	1.251
6	-0.284	0.057	-0.068	1.183
7	-0.341	0.079	-0.082	1.101
8	-0.419	—	-0.101	1.000

Table 3.1-2: Factor Loadings for the UFS-QoL Symptom Severity Scale in TAK-385/CCT-001

Items		Factor1	Factor2	Factor3
Q2	Passing blood clots during your period	0.763	0.105	0.073
Q1	Heavy bleeding during your period	0.759	0.091	0.123
Q5	Feeling tightness or pressure in pelvis	0.467	0.175	0.167
Q8	Feeling fatigued	0.399	0.288	0.078
Q6	Frequent urination in daytime	0.114	0.965	0.069
Q7	Frequent nighttime urination	0.212	0.630	0.013
Q4	Fluctuation in length of monthly cycle	0.039	0.092	0.995
Q3	Fluctuation in duration of menstruation	0.178	0.003	0.416

Extraction method: maximum likelihood. Rotation method: orthogonal.

3.2. Development of the Bleeding and Pelvic Discomfort Scale Using Confirmatory Factor Analysis Based on Phase 3 Data

The exploratory factor structure arising from the phase 2 data was assessed using data from the phase 3 studies MVT-601-3001 and MVT-601-3002.

Analyses were based on pooled, blinded data from the first one third of patients enrolled in the two phase 3 studies of relugolix in uterine fibroids (MVT-601-3001 and MVT-601-3002), who completed the patient global assessment of symptoms (PGA) and the Uterine Fibroid Symptom and Health-Related Quality of Life (UFS-QoL) at Baseline and at Week 24.

